9.4 Data Sources

Source documents are defined as original documents. The investigator will document patient data in his/her own patient files which will serve as source data for the study. Data are collected from the source documents for each patient in the study, consisting of medical records containing demographic data, medical, treatment and diagnostic documentation and laboratory assessments.

The investigator(s)/institution(s) will permit study-related monitoring, audits, independent ethics committee/- review board (IEC/IRB) review, and regulatory inspection(s), providing direct access to source data documents.

9.4.1 Data to be Documented

This observational study covers three documentation periods, see Figure 1. An overview on data to be collected throughout the study is summarized in **Table 2**.

After the patient has signed the patient authorization form, the following data will be documented in the eCRF, if available from the patient charts based on assessments done in physicians' routine clinical practice.

9.4.1.1 Inclusion Documentation

The following will be documented:

- Demographic information
 - Interleukin 28B (IL28B) genotypes
- CHC disease characteristics
 - Year of diagnosis and mode of infection
 - Stage of liver fibrosis
- CHC treatment history
 - Naïve or experienced
 - If experienced, most recent prior therapy and outcome
- Relevant medical history, co-morbidities and co-infections
- Concomitant medication, see 9.4.1.5

Confidential Information

- ABBVIE REGIMEN ± RBV
- Laboratory data

Key clinical chemistry	Remarks
▪ ALT (alanine-aminotransferase)	including upper limit of normal (ULN),
▪ AST (aspartate-aminotransferase)	including ULN, AST to platelet ratio index (APRI) and Fibrosis-4 Score/Index (FIB-4)* will be calculated
▪ γ-GT (gamma-glutamyltransferase)	
▪ Total bilirubin	
▪ Albumin	
▪ Creatinine	creatinine clearance [‡] will be calculated
▪ AFP	
Key hematology	
▪ Hb (Hemoglobin)	
▪ Platelets	
▪ Prothrombin time	or international normalized ratio (INR)
Virology	
▪ HCV genotype and subtype	
▪ HCV RNA	quantitative/ qualitative HCV RNA by polymerase chain reaction (PCR) test, see 9.4.1.4
HIV-infected patients only	
▪ CD 4 count (cluster of differentiation 4)	most recent assessment
▪ HIV RNA	in copies/mL

*derived from patient's age, ALT, AST and platelets

‡by Cockcroft-Gault-Formula based on creatinine, gender, age and weight

- Patient questionnaires, see table 2 and 9.4.1.6

9.4.1.2 During Treatment Documentation

Follow-up visits are scheduled by the physician per routine clinical practice. Likewise treatment, procedures and diagnostic methods will follow physicians' routine clinical practice.

The following will be documented:

- Laboratory data

Key clinical chemistry	Remarks

▪ ALT▪ AST	including ULN including ULN, APRI and FIB-4 will be calculated

▪ γ-GT▪ Total bilirubin▪ Creatinine	creatinine clearance will be calculated
Key hematology	

▪ Hb▪ Platelets	
Virology	

▪ HCV RNA	quantitative/ qualitative HCV RNA PCR test, see 9.4.1.4
HIV-infected patients only	

▪ CD 4 count▪ HIV RNA	most recent assessment in copies/mL

- Concomitant medication, see 9.4.1.5
- Adherence to ABBVIE REGIMEN \pm RBV (ABBVIE REGIMEN - % of target dose taken and RBV)
- Tolerability (sAEs and AEs, see 0) and pregnancies (see 0)
- Patient questionnaires see 9.4.1.6

9.4.1.3 Post-Treatment Documentation

Follow-up visits are scheduled by the physician per routine clinical practice. Likewise treatment, procedures and diagnostic methods will follow physicians' routine clinical practice.

The following will be documented:

- Laboratory data

- Key clinical chemistry

- ALT
 - AST

- Remarks

- including ULN
including ULN,
APRI and FIB-4, will be calculated

- γ -GT
 - Total bilirubin
 - Albumin
 - Creatinine

- creatinine clearance will be calculated

- Key hematology

- Hb
 - Platelets
 - Prothrombin time

- or INR

- Virology

- HCV RNA

- quantitative/ qualitative HCV RNA PCR test, see 9.4.1.4

- HIV-infected patients only

- CD 4 count
 - HIV RNA

- most recent assessment
in copies/mL

- Tolerability (sAEs, see 0) and pregnancies (see 0)
- Patient questionnaires see 9.4.1.6

Confidential Information

No use or disclose outside AbbVie is permitted without prior written authorization from AbbVie

Table 2 - Data Documentation Schedule

Assessment/ Procedure (only available data to be collected; no diagnostic or monitoring procedures to be applied to the patients apart from those of routine clinical practice)	Baseline	Treatment Period			Post-treatment (PT) Period		
		On-treatment visits	Mid treatment visit for pts receiving 24 weeks of therapy	EoT ^b	Early PT visit	SVR 12 visit	SVR 24 visit
Patient authorization	X ^a						
Demographic information	X						
IL28B	X						
Relevant CHC disease characteristics	X						
Liver fibrosis stage	X						
CHC treatment history	X						
HCV genotype and subtype	X						
HCV RNA samples	X	X	X	X	X	X	X
Clinical chemistry and hematology	X	X	X	X	X	X	X
ABBVIE REGIMEN initiation documentation	X						
ABBVIE REGIMEN adherence		X	X	X			
Concomitant medication	X	X	X	X			
Relevant medical history, co-morbidities	X						
sAE, AE and pregnancy reporting	X	X	X	X	X ^c	X ^d	X ^d
For patients receiving RBV: Evidence, in accordance with local label, that female patient or female partner of male patient is not pregnant	X						
Patient questionnaires – WPAI, EQ5D-5L	X			X		X	X

Abbreviations: EoT = End of Treatment (at Week 12 or 24 or at premature discontinuation), PT = Post-Treatment

- a Written patient authorization must be obtained before any data documentation in the eCRF
- b Patients who prematurely discontinue should return to the site to document EoT data
- c Tolerability documentation until PT week 4
- d Pregnancy reporting for patients treated with DAA plus RBV

9.4.1.4 HCV RNA Sample

HCV RNA sample – the following needs to be documented:

- **Quantitative HCV RNA by PCR test**
 - Test name and result in IU/mL
 - Lower limit of detection (LLoD) in IU/mL and lower limit of quantification (LLoQ) in IU/mL
- **Qualitative HCV RNA by PCR test**
 - Test name and result (positive/negative)
 - LLoD in IU/mL

Confidential Information

9.4.1.5 Concomitant Medication

Concomitant medication - the following will be documented:

- Concomitant medication used from the time when the decision is made to initiate treatment with the ABBVIE REGIMEN until after the last dose

It should be verified by the treating physician that concomitant medication can be safely administered with the ABBVIE REGIMEN (including ritonavir) and RBV. Some medications may be contra-indicated, some may require dose adjustments due to potential for drug-drug interactions (DDIs). The investigator or qualified designee should review the concomitant medication(s) labels and screen concomitant medications at each visit for potential DDIs.

9.4.1.6 Standardized Assessment Tools

This study will assess quality of life and work productivity using PRO instruments: EQ-5D-5L and WPAI Hep C. Validated translations of these patient questionnaires will be administered.

Assessment of general quality of life - EQ-5D-5L

The EQ-5D-5L is a health state utility instrument that evaluates preference for health status (utility). The 5 items in the EQ-5D-5L comprise 5 dimensions (mobility, self-care, usual activities, pain/discomfort, and anxiety/depression) each of which are rated on 5 levels of severity. Responses to the 5 items encode a discrete health state which is mapped to a preference (utility) specific for different societies. Patients also rate their perception of their overall health on a separate visual analogue scale (VAS).

The EQ-5D-5L should require approximately 5 minutes to complete and is presented in Annex 1.

Assessment of work productivity and activity impairment – WPAI Hep C V2.0

The WPAI questionnaire will be used to measure work absenteeism, work presenteeism, and daily activity impairment. The WPAI questionnaire was created as a patient-reported quantitative assessment of both reduced productivity at work and non-work activities. WPAI has been validated as a general health measure (WPAI-GH) and can be easily modified for specific health condition, disease or problem (WPAI-SHP). WPAI Hep C V2.0 is the HCV specific questionnaire that will be used in this study). Respondents are asked about time missed from work and time while at work during which productivity was impaired in the past seven days. Results of WPAI

are expressed as a percentage of impairment from 0 to 100, with higher percentages indicating greater impairment and less productivity:

- % Presenteeism – percentage of impairment while working due to health problem
- % Absenteeism – percentage of work time missed due to health problem
- % Total work productivity impairment (TWP) – percentage of overall work impairment due to health problem
- % Total activity impairment (TAI) – percentage of general (non-work) activity impairment due to health problem

The WPAI Hep C should require approximately 5 minutes to complete and is presented in Annex 2.

PRO data are not considered a potential source of adverse reactions. However, participating sites should review the PRO data and if a possible product-related event (including a suspected adverse reaction) is noted, the health care provider (HCP) must determine whether the event is related to paritaprevir/r – ombitasvir ± dasabuvir (or any other AbbVie authorized product) and if so, it should be reported to AbbVie. The relevant AbbVie Pharmacovigilance contact details are specified in Section 11.0.

9.5 Study Size

In phase III studies investigating the interferon-free ABBVIE REGIMEN ± RBV, SVR12 rates of at least 90% were observed, even in difficult-to-treat CHC patients (e.g. cirrhotic G1a treatment experienced patients). It is expected that 400 patients treated with the ABBVIE REGIMEN ± RBV can be included into this observational study during the planned inclusion period of 6 months, and that about 90 to 95% of the patients enrolled will be evaluable in the core population (see Section 9.7.1 for the definition of the core population). As shown in **Table 3**, if the SVR12 rate is at least 90% and there are 360-380 evaluable patients, then the width of the 95% confidence interval (CI) will not be wider than 6.5%. If the SVR12 rate is at least 95% and there are 360-380 evaluable patients, then the 95% CI will have a width of less than 5%. With at least 340 evaluable patients the width is still less than 5%, if the SVR12 rate is at least 95%.

Table 3 Width of 95% Confidence Interval for SVR12

Number of patients	SVR12 rates	95% Confidence Interval*		
		Lower Limit	Upper Limit	Width
340	90%	86.3	93.0	6.7%
340	95%	92.1	97.1	4.9%
360	90%	86.4	92.9	6.5%
360	95%	92.2	97.0	4.8%
380	90%	86.5	92.8	6.3%
380	95%	92.3	97.0	4.7%

* exact two-sided 95% confidence interval according to Clopper-Pearson

9.6 Data Management

9.6.1 Electronic Case Report Forms

Data for this study will be recorded in English by each participating center via an electronic data capture (EDC) system using a web-based eCRF. Examinations, diagnostic measures, laboratory assessments, findings and observations routinely performed in patients with CHC included in this cohort, will be transcribed by the investigator or designee from the source documents into the eCRF. Only data specified in the protocol will be entered into the eCRF. For each enrolled patient, the investigator or designee will create a new patient file in the eCRF and a unique patient number will be automatically allocated by the system.

A comprehensive data validation program utilizing front-end checks in the eCRF will validate the data. Automated checks for data consistency will be implemented, discrepancies need to be solved by the researcher in the eCRF before the module can be completed.

Follow-up on eCRF data for medical plausibility will be done by AbbVie personnel (or their representatives). Queries will be generated in the eCRF for online resolution at the site. The investigator or an authorized member of the investigator's staff will make any necessary data corrections to the eCRF. All change information, including the date and person performing the corrections, will be available via the audit trail, which is part of the EDC system. The principal investigator of each site will finally review the eCRFs for completeness and accuracy of available data and provide his or her electronic signature and date to the eCRFs as evidence thereof.

Access to the EDC system will be provided for the duration of the study through a password-protected method of internet access. Such access will be removed from investigator sites at the end of the site's participation in the study. Data from the EDC

Confidential Information

No use or disclose outside AbbVie is permitted without prior written authorization from AbbVie

system will be archived on appropriate data media (e.g. CD-ROM) and provided to the investigator as a durable record of the site's eCRF data.

Original Questionnaires will be sent from the participating site to:

9.6.2 Assignment of Preferred Terms

AEs will be coded using the Medical Dictionary for Regulatory Activities (MedDRA) and will be tabulated by primary MedDRA system organ class (SOC) and preferred term (PT). For treatments, surgical and medical procedures the international non-proprietary name (INN) Drug Terms and Procedures Dictionary will be used.

9.7 Data Analysis

9.7.1 Analysis Population, Time Windows and Handling of Missing Data

The target population (TP) is defined as all patients who fulfill the criteria specified in Section 9.2.1. The core population (CP) is defined as all patients of the TP, who have started the treatment combination recommended in the current local label for their disease characteristics. Patients not receiving the treatment recommended in the local label will be summarized in the non-core population (NCP). In addition, the core population with sufficient follow-up data (CPSFU) is defined as all CP patients, who fulfil one of the following criteria:

- (1) evaluable HCV RNA data ≥ 70 days after the last actual dose of the ABBVIE REGIMEN (i.e. data within the SVR12 time window)
- (2) a HCV RNA value ≥ 50 IU/mL at the last measurement post-baseline (i.e. no virological response achieved at the last measurement on-treatment or post-treatment)
- (3) HCV RNA < 50 IU/mL at the last measurement post-baseline, but no HCV RNA measurement ≥ 70 days after the last actual dose of the ABBVIE REGIMEN due to reasons related to safety (e.g. dropped out due to AE) or incomplete efficacy information (e.g. virologic failure such as relapse is reported in the eCRF but date and value of the corresponding HCV RNA test

Confidential Information

is missing). This means only patients who had virological response at their last on-treatment or post-treatment measurement, but had no HCV RNA measurements ≥ 70 days post-treatment for reasons not related to safety or effectiveness (e.g. lost-to-follow-up or patient not willing to perform an additional HCV RNA test ≥ 70 days post-treatment) will be excluded from this analysis.

The Safety Population (SP) is defined as all patients who received at least one dose of the ABBVIE REGIMEN.

In accordance with the non-interventional nature of the study all HCV RNA measurements will be performed at the sole discretion of the physician and all HCV RNA measurements have to be entered into the eCRF. All recorded HCV RNA values will be assigned to appropriate time points (baseline, on-treatment visits, EoT visit, post-treatment visits). The time windows for the assignments will be specified in the statistical analysis plan (SAP).

No data will be imputed for any effectiveness or safety analyses except for the analyses of the HCV RNA endpoints. When there is no HCV RNA value in a visit time window post-baseline, but prior to EoT, the closest values before and after the window, regardless of the value chosen for the subsequent and preceding window, will be used for the flanking imputation described below. If a patient has a missing HCV RNA value at a post-baseline visit prior to EoT but has undetectable HCV RNA (with LLoD ≤ 50 IU/mL) or unquantifiable, but detectable HCV RNA levels (with LLoQ ≤ 50 IU/mL) at both the preceding and succeeding measurements, the HCV RNA level will be considered undetectable or unquantifiable, respectively, at this visit for this patient. In addition, if a patient has an unquantifiable HCV RNA level at the preceding measurement and an undetectable HCV RNA level at the succeeding measurement, or vice versa, the HCV RNA level will be imputed as unquantifiable at this visit for this patient. For virological response at EoT a corresponding backward imputation approach will be applied. This means if HCV RNA is missing at EoT, then unquantifiable or undetectable will be assumed for EoT, if the succeeding HCV RNA value is undetectable or unquantifiable. For SVR12 the single last available HCV RNA measurement ≥ 70 days post-treatment will be used. Subsequent to this flanking and backward imputation, if the HCV RNA value remains missing at a specific time point, then the patients will be considered as virological failure at this time point (i.e. not undetectable or unquantifiable).

9.7.2 Demographics and Disease Characteristics

All baseline and disease characteristics will be summarized for the CP stratified by the CP analysis groups (i.e. based on genotype 1 subtype, fibrosis status, treatment experienced or naïve), which are relevant for scheduled treatment combination

Confidential Information

No use or disclose outside AbbVie is permitted without prior written authorization from AbbVie

(ABBVIE REGIMEN ± RBV) and duration (12 and 24 weeks). In addition, baseline summaries will be repeated for the SP and the TP without stratification into subgroups. Summary statistics (n, mean, median, standard deviation [SD], and range) will be generated for continuous variables (e.g. age and body mass index [BMI]). The number and percentage of patients will be presented for categorical variables (e.g. gender and race). Further details of analysis populations and the CP analysis groups will be specified in the SAP, taking into account the ABBVIE REGIMEN recommended in the current local label for various patient groups.

9.7.3 Effectiveness Analysis

The primary effectiveness analysis on clinical outcomes will be performed on all patients in the CP stratified by the CP analysis groups. Due to the non-interventional nature of this study several different methods for determination of the HCV RNA value can be applied. For the purpose of the statistical analysis, a HCV RNA measurement is considered ≤ 50 IU/mL,

- if a PCR test was used
- and the test result is undetectable and the LLoD of the test is ≤ 50 IU/mL or the test result is unquantifiable and the LLoQ is ≤ 50 IU/mL

9.7.3.1 Primary Effectiveness Endpoint

The percentage of patients achieving SVR12 (single last HCV RNA < 50 IU/mL 12 weeks [i.e. at least 70 days] after the last actual dose of the ABBVIE REGIMEN) is the primary effectiveness endpoint.

9.7.3.2 Secondary Effectiveness Endpoints

The secondary effectiveness endpoints are:

- The percentage of patients with virological response (HCV RNA < 50 IU/mL) at EoT
- The percentage of patients with relapse (defined as HCV RNA < 50 IU/mL at EoT followed by HCV RNA ≥ 50 IU/mL)
- The percentage of patients with breakthrough (defined as at least one documented HCV RNA < 50 IU/mL followed by HCV RNA ≥ 50 IU/mL during treatment).
- The number and percentage of patients meeting each and any of the following SVR12 non-response categories:

Confidential Information

- On-treatment virologic failure (breakthrough [defined as above] or failure to suppress [each measured on-treatment HCV RNA value ≥ 50 IU/mL])
- Relapse (defined as HCV RNA < 50 IU/mL at EoT or at the last on-treatment HCV RNA measurement followed by HCV RNA ≥ 50 IU/mL post-treatment)
- Premature study drug discontinuation with no on-treatment virologic failure
- Missing SVR12 data and/or none of the above criteria

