9.9 Limitations of the Research Methods

The limitations of observational studies, such as uncontrolled confounding by lack of randomization, and difficulties to clearly interpret treatment effects in the context of missing data are well known. Their validity can be increased by accurate outcome measurements, documentation of the most common confounders, sufficient length of follow-up and by activities to obtain complete recording of available data as well as by searches for missing key data.

The most important outcome measure in this study is HCV RNA. Missing or unrecorded follow-up HCV RNA data can in particular lead to an underestimation of the real SVR rate as compared to the SVR rate of interventional trials. Highly sensitive and quantitative diagnostic tests are required to measure HCV RNA levels in blood. In an observational study each center will be using its own test – either commercially available or so-called “home-brew” tests – which might change from one visit to the next within a patient data set. The challenge is to accurately and consistently document test properties such as the LLoD and the LLoQ to put the results into perspective of prior outcomes from randomized controlled trials with (usually) central laboratory assessments for all trial participants.

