# 4.2.7.2 Secondary Variables

# 4.2.7.2.1 Secondary Effectiveness Variables

#### Response

For the other response rates (i.e. RVR, SVR24, EoT response rate, relapse rate, viral breakthrough), the simple percentage of patients and a two-sided 95% confidence interval (CI) of the percentage will be computed (based on the Wilson's score method) as well. The RVR and EoT response rates will be reported for CP and the SVR24 rate will be reported for the respective CPSFU, stratified by genotype and cirrhosis status and overall. The relapse rates will be estimated stratified by SVR window (i.e. during SVR12 window=relapse12, during SVR24

window=relapse24) and stratified by genotype and cirrhosis status and overall in patients of the CP with EoT response who fulfilled the following criteria:

- completed treatment as defined previously.
- had at least one HCV RNA measurement >= 70 days post-treatment or was a treatment failure between EoT and 70 days post-treatment.

Viral breakthrough rates [defined as at least one documented HCV RNA <50 IU/mL followed by HCV RNA ≥50 IU/mL during treatment] will be estimated overall and stratified by genotype and cirrhosis status in all patients of the CP, who have at least one undetectable or unquantifiable, ontreatment HCV RNA measurement and at least one on-treatment or EoT measurement thereafter.

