#### Non-Response

In another table, the numbers and the percentages of the SVR12 non-responder categories and responder will be summarized for CP patients, overall and stratified by genotype and cirrhosis status. The following SVR12 non-response categories will be considered:

- On-treatment virologic failure (breakthrough [defined as at least one documented HCV RNA <50 IU/mL followed by HCV RNA ≥50 IU/mL during treatment] or failure to suppress [each measured on-treatment HCV RNA value ≥50 IU/mL])
- Relapse (defined as HCV RNA <50 IU/mL at EoT or at the last on-treatment HCV RNA measurement followed by HCV RNA ≥50 IU/mL post-treatment and completed treatment as defined previously)
- Death and none of the above
- Premature study drug discontinuation with no on-treatment virologic failure and none of the above
- Insufficient virological response, other than those mentioned above (patients for whom
  insufficient virological response was reported, or who had HCV RNA >=50 IU/mL post
  EoT and no HCV RNA test on treatment) and none of the above
- Missing SVR12 data and/or none of the above criteria

Virological response rates and non-response categories will be displayed for patients who completed treatment with AbbVie regimen, as well.

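### Viral breakthrough is scored from one unconfirmed on-treatment HCV RNA value of 50 IU/mL or more, even when the next value is again below 50

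*Protocol*

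**What the plan says.** Protocol 9.7.3.2 lists breakthrough as a secondary endpoint, defined as "at least one documented HCV RNA < 50 IU/mL followed by HCV RNA ≥ 50 IU/mL during treatment". SAP 4.1.2 repeats the rule, as does SAP 4.2.7.2.1 under Response: "Viral breakthrough rates [defined as at least one documented HCV RNA <50 IU/mL followed by HCV RNA ≥50 IU/mL during treatment". The rate has its own output table (SAP Table 8). Neither document asks for a repeat test, a minimum rise, the same assay, or a next value that stays at 50 or above.

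The same flag feeds the first SVR12 non-response category. SAP 4.2.7.2.1, Non-Response, reads: "On-treatment virologic failure (breakthrough [defined as at least one documented HCV RNA <50 IU/mL followed by HCV RNA ≥50 IU/mL during treatment". How that category relates to the others varies:

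- The protocol asks for "The number and percentage of patients meeting each and any of the following SVR12 non-response categories", which does not make the categories exclusive.
- The SAP's relapse category requires a value "followed by HCV RNA ≥50 IU/mL post-treatment and completed treatment as defined previously". It does not exclude on-treatment failure.
- Early stopping does exclude it: "Premature study drug discontinuation with no on-treatment virologic failure and none of the above". The protocol's version also excludes on-treatment failure. In the SAP, death and other insufficient response apply only if no earlier category does.
- The last category is "Missing SVR12 data and/or none of the above criteria", which can be read either way.

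Protocol 9.9 says that each centre uses its own commercial or in-house test, "which might change from one visit to the next within a patient data set". Protocol 9.7.1 leaves testing to the physician and requires every value to be entered.

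**The concern.** A breakthrough rate should describe virus that returned on treatment. Here one reading settles the matter, and a later reading that contradicts it is ignored. With mixed local tests, a single value just across 50 IU/mL may reflect the assay rather than the virus. Protocol 9.7.3 and SAP 4.2.3 accept an undetectable or unquantifiable result as 50 or below only if the test's limit is itself 50 or below. They do not say how such a result from a less sensitive test is classed, so a change of test could also create an apparent crossing.

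The error from a false high reading has one direction: it can add a breakthrough but never remove one. More tests give more chances, and 24-week patients have an extra mid-treatment visit. The rule also sits oddly beside the imputation in Protocol 9.7.1 and SAP 4.2.3, where a missing value between two negative values is taken as negative.

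Two outputs are at stake: the breakthrough rate, and the table that explains why patients failed to reach SVR12.

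**Working it through.** **The plan's own figure.** The documents give no expected breakthrough rate, false-reading rate or number of tests per patient. The nearest stated figure is the interval width in Protocol Table 3. Clopper-Pearson at n = 360 gives 86.43 to 92.90 for 90% (width 6.47; stated 6.5) and 92.21 to 97.01 for 95% (width 4.80; stated 4.8). The table reproduces. Only the planned 360-380 evaluable patients are carried forward.

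**The rule applied to patterns** (IU/mL):

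| Values | Breakthrough? | SVR12 | Other category met |
|---|---|---|---|
| <50, 60, <50 at EoT; <50 at SVR12 | Yes | Responder | None |
| <50, 60 as last on-treatment value; <50 at SVR12 | Yes | Responder | None |
| <50, 60, <50 at EoT; treatment completed; ≥50 afterwards | Yes | Non-responder | Relapse as well |
| <50, 60, <50 at EoT; treatment completed; then lost | Yes | Failure by imputation | Missing data, depending on how and/or is read |
| <50, 60, <50; stopped early; no later value | Yes | Failure by imputation | Premature discontinuation ruled out by its own wording |

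**Size among all patients.** Inputs: N = 360-380 (Protocol 9.5). Assumed: p, the chance that a later on-treatment test gives a spurious value of 50 or more, is 0.2%, 0.5% or 1%; k, the number of on-treatment tests after the first value below 50, is 1 or 2; readings are independent; and all N patients enter the breakthrough denominator.

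Expected false breakthroughs = N × (1 − (1 − p)^k).

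| p | k = 1 | k = 2 |
|---|---|---|
| 0.2% | 360 × 0.002 = 0.72 to 380 × 0.002 = 0.76 | 360 × 0.003996 = 1.4 to 380 × 0.003996 = 1.5 |
| 0.5% | 1.8 to 1.9 | 360 × 0.009975 = 3.6 to 380 × 0.009975 = 3.8 |
| 1% | 3.6 to 3.8 | 360 × 0.0199 = 7.2 to 380 × 0.0199 = 7.6 |

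The range is 0.7 to 7.6 patients, or 0.2% to 2.0%.

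**Size among non-responders.** Only these patients can enter the non-response table. At 95% SVR12 there are 360 × 0.05 = 18 to 380 × 0.05 = 19; at 90%, 36 to 38. Applying the same probabilities, and assuming spurious readings are equally likely in responders and non-responders:

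- 95% SVR12: 18 × 0.002 = 0.04 to 19 × 0.0199 = 0.38 patients
- 90% SVR12: 36 × 0.002 = 0.07 to 38 × 0.0199 = 0.76 patients

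Both ranges stay below one patient.

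**Effect of confirmation.** If two consecutive on-treatment values must be 50 or more, the false rate is about (k − 1)p². At p = 1% and k = 2 this is 0.0001, or 380 × 0.0001 = 0.04 patients. A spurious last value with nothing after it would still count under the rule proposed below.

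**The case against.** The strongest reply is that the size is unknown and may be trivial. Neither p nor k is in the documents. SAP Table 3 names only week 4 and EoT as on-treatment HCV RNA time points, so for a 12-week patient one later value is at least as plausible as two. Protocol 9.9 says that tests might change, not that spurious crossings are expected. The plan also records each test's limits (Protocol 9.4.1.4) and sets conditions on them. All of this stands: the figures are illustrative.

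The plan also relies on single values elsewhere. Protocol SVR12 uses the last one, and relapse needs no confirmation. In a non-interventional study, confirmation depends on whatever repeat values exist. That limits what a rule can do, but it does not justify ignoring a contradicting value already in the database.

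A reader might infer that the definition moves relapsers and lost patients out of their proper categories. The documents do not establish this. Relapse carries no exclusion of on-treatment failure, and the missing category's and/or leaves room for double counting. These patients enter on-treatment failure, but they leave the other category only under a first-match hierarchy that neither document states. Displacement is explicit only for premature discontinuation (both documents) and for death and insufficient response (SAP).

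**Conclusion.** The definitional gap is real and is present in both documents: a single on-treatment value of 50 or more after a value below 50 makes a breakthrough whatever follows. It can count SVR12 responders as breakthroughs, and a false high reading can only push the rate up.

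On the stated assumptions the effect is about 0.7 to 7.6 false breakthroughs among 360-380 patients, falling mostly on the standalone rate. It is tempting to set 7.6 against the 18-19 failures expected at 95% SVR12 and conclude that the reasons for failure would be badly misstated. That comparison does not hold, because most of the false breakthroughs would be responders; fewer than one non-responder is expected to be affected. Primary SVR12 is judged on post-treatment values and does not change. No decision rule depends on the breakthrough rate, and the analyses are descriptive and exploratory. The severity is minor.

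**What to change.** In Protocol 9.7.3.2 and SAP 4.1.2 and 4.2.7.2.1:

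- Count breakthrough only if the next available HCV RNA value, on or after treatment but before any new HCV treatment, is also 50 IU/mL or more, or if no later value exists.
- Use the same flag in the non-response table.
- Report values of 50 or more followed by a value below 50 on a separate line, labelled transient.
- State whether the non-response categories are a first-match hierarchy or may overlap.

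The cost is SAP and protocol wording, one derived flag and one extra table line. No additional testing is needed. The downside is that a true rebound that is later re-suppressed moves to the transient line, where it remains visible.
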